5.5.1 Analysis of Primary Efficacy Endpoint

The primary efficacy endpoint is defined as time-weighted average (TWA) change in log10-transformed viral load by RT-qPCR from baseline to Day 8, where TWA will be derived using the trapezoidal rule:

$$\frac{\sum_{i=a}^{b-1} \{0.5 \times (Y_i + Y_{i+1}) \times (t_{i+1} - t_i)\}}{(t_b - t_a)}$$

Y_i is the change from baseline in log10-transformed viral load by RT-qPCR at Visit i , t is the actual study day at the specified timepoint, a is the baseline visit at Day 1, and b is the Day 8 visit.

At the final analysis, each dose of the RD-X19 device will be compared to sham using an Analysis of Covariance (ANCOVA) model with baseline viral load on log10 scale as a covariate and treatment group as an independent variable.

An example of SAS code for the analysis is as follows:

```
proc glm data=datain;
  class trt;
  model aval = trt base /ss3;
  estimate '4x RD-X19 vs Sham' trt 1 0 -1;
  estimate '7x RD-X19 vs Sham' trt 0 1 -1;
  lsmeans trt /pdiff stderr cl;
run;
```

where AVAL denotes the variable to be analyzed, BASE denotes the covariate baseline value, and TRT denotes treatment group with values 1 for 4 Days RD-X19, 2 for 7 Days RD-X19, and 3 for Sham.

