9.3 Efficacy Assessments

Efficacy comparisons will be made in the ITT Population with the intent of estimating the effect of the RD-X19 device relative to sham in several outcome measures. Subjects will be instructed to fill out diary cards twice daily to assess their symptoms associated with disease progression and record the number of treatments completed. Additionally, at Baseline and days 3, 5, and 8, subjects will provide two saliva specimens and an oropharyngeal swab for virology endpoint assessments. One saliva specimen will be collected, preserved, and shipped fresh to a central lab for assessment of SARS-CoV-2 mRNA via RT-qPCR. The second specimen and the oropharyngeal swab will be collected in separate collection tubes, frozen, and stored at the site and shipped to a central lab at the end of each cohort.

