9.3.1 Efficacy assessments

Various endpoints will explore the impact of RD-X19 treatment on the reduction in log10 SARS-CoV-2 viral load and alleviation of symptoms associated with COVID-19. Both the magnitude of reduction as a function of dose as well as time to clearance will be assessed in support of the primary efficacy analysis. Subjects will be instructed to fill out a diary card or electronic equivalent to assess their signs and symptoms of disease twice daily. Each of the eight symptoms will be rated on a scale from none (0) to severe (3).

- Time weighted average change in viral load from baseline by RT-qPCR from Day 1 to Day 8
- Geometric mean viral load as measured in saliva on day 1, 3, 5, and 8 by RT-qPCR
- Proportion of subjects demonstrating viral load reduction $\geq 95\%$ by RT-qPCR (at each visit)
- Time to undetectable viral load in saliva by RT-qPCR.
- Proportion of subjects demonstrating clearance of viral infection, defined as a negative test via RT-qPCR on Day 8/ET.
- Median time to alleviation of symptoms,
 - The time to alleviation of symptoms endpoint, is defined as the time when all eight symptoms (cough, sore throat, nasal congestion, headache, chills/sweats, muscle or joint pain, fatigue, and nausea) had been assessed by the subject as none or mild.
- Change in COVID-19 Severity Score from baseline
 - The COVID-19 Severity Score is defined as the sum of all the individual symptom severity scores divided by the total number of symptoms assessed (8).
- Viral load by viral titer (at each visit)

- The paired oropharyngeal swab and saliva sample from each subject at each visit allows for independent analysis via two different live virus sampling methodologies and also a direct paired sample comparison of the viral load present in the back of the throat versus saliva.

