10 STATISTICAL CONSIDERATIONS

10.1 Statistical Hypotheses

This is a randomized, ascending dose finding study. The primary goal of the study is to evaluate the safety and efficacy of the RD-X19 device in SARS-CoV-2 infected individuals with uncomplicated COVID-19.

10.2 Power and Sample Size:

This is a double-blind study and hypothesis generating in nature. The sample size was selected for convenience.

Subjects will be randomized to treatment arm within dose in a 2:1 ratio according to a fixed schedule using a permuted block design and stratified by clinical site. The target number of subjects randomized per dose is 30 (20 subjects to the RD-X19 arm, 10 subjects to the sham arm).

One interim analysis is planned at the end of Cohort 1.

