3.1 Study Design

For the purpose of exploring the above objectives, the study will be conducted as a randomized, double-blind, sham-controlled dose escalation study in SARS-CoV-2 infected individuals with outpatient COVID-19 at two dosing schedules.

This study plans to enroll into two treatment arms within two escalating dose cohorts:

Volunteers meeting all inclusion criteria and none of the exclusion criteria will be randomized to the RD-X19 treatment arm or the sham treatment arm within each cohort in a 2:1 ratio (20 RD-X19 : 10 sham), according to a fixed schedule via a permuted block design and stratified by clinical site. Light will be administered twice daily locally to the mouth and throat only for four days for Cohort 1 and for seven days for Cohort 2.

The clinic visits will occur at:

- Visit 1 / Screening, Enrollment & Randomization

- Visit 2 / Day 2
- Visit 3 / Day 3
- Visit 4 / Day 5 (\pm 1 day)
- Visit 5 / Day 8 (\pm 1 day) / Early Termination (ET)

Assessments of treatment response will occur on study days 3 and 5, with a final determination of efficacy made on day 8 (inclusive).

Efficacy will be evaluated through evaluation of viral load through quantitation of SARS-CoV-2 mRNA by RT-qPCR and via quantitation of replication competent virus by viral titer. Severity of the symptoms of disease will also be aggregated to produce a composite COVID-19 severity score. Safety and tolerability assessments will include solicited and unsolicited adverse events (AEs), physical examinations, vital signs, and clinical laboratory tests.

One unblinded interim analysis is planned upon completion of all subjects in Cohort 1. The results of the interim analysis will be reviewed by a safety monitoring team and a recommendation will be made to the sponsor on whether enrollment should proceed for the next cohort at the next planned dose or at a reduced dosing frequency (e.g. once daily). The study is designed to evaluate at least 2 dosing schedules, ascending, or descending based on safety of each previous cohort.

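### The trial is called dose finding, but the SAP specifies and tabulates only each schedule against a pooled sham; no between-schedule estimate built on the concurrent shams is planned

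*Combined protocol and SAP*

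**What the plan says.** Protocol 10.1 states: "This is a randomized, ascending dose finding study". Protocol 6.1 also describes the design as dose finding. Protocol 9.3.1 says, in support of the primary efficacy analysis: "Both the magnitude of reduction as a function of dose as well as time to clearance will be assessed".

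SAP 3.1 has light "administered twice daily locally to the mouth and throat only for four days for Cohort 1 and for seven days for Cohort 2". Randomisation is 20:10 within each cohort.

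For the primary endpoint, SAP 5.5.1 says that "each dose of the RD-X19 device will be compared to sham using an Analysis of Covariance (ANCOVA) model". The sample code gives treatment three levels: 4-day, 7-day and a single sham level. It has two ESTIMATE statements, each a schedule minus sham. An LSMEANS statement follows with PDIFF and CL and no control level named. Table 14.2.1.1 shows the LS mean of each of the three groups, but differences, confidence intervals and p-values only for RD-X19 v sham.

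The interim-analysis section of the SAP treats Cohort 1 as in effect a separate study, unconnected with Cohort 2. SAP 5.1 says that the study is not powered for testing and that p-values are descriptive.

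**The concern.** The protocol makes dose a question, and the reporting plan has no line that answers it. A reader of Table 14.2.1.1 will see two v-sham results side by side and may take a difference between their p-values as a dose effect, which it is not.

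The one between-schedule figure that the sample code would produce is the wrong one to rely on. It sets 7-day subjects from the later cohort against 4-day subjects from the earlier one. Any shift between cohorts in case mix, timing or laboratory conditions goes into it in full. Each cohort has its own randomised sham group, which could remove such a shift, but the three-level coding does not use it for that purpose.

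**Working it through.** The plan states no SD, effect size, alpha or power, so there is no figure of its own to reproduce beyond 2 × (20 + 10) = 60, which agrees.

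**What each contrast estimates.** Let δ be a shift that affects everyone in Cohort 2.
- Planned output: the pooled sham mean cancels, because (7-day − sham) − (4-day − sham) = 7-day − 4-day. The point estimate can therefore be had by subtraction in Table 14.2.1.1, but not its CI. It contains the schedule effect plus δ. Sham subjects contribute only to the residual variance and the baseline slope.
- Concurrent-sham contrast: (7-day + δ − Cohort 2 sham − δ) − (4-day − Cohort 1 sham). The δ cancels.

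**Precision**, in units of the residual SD of TWA, assumed common to all groups:

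| Contrast | SE at 20:10 | 95% half-width at 20:10 | 95% half-width at 24:12 |
|---|---|---|---|
| Direct 7-day v 4-day | √(2/20) = 0.316 | 0.63 (56 df) | 0.58 |
| Concurrent-sham | √(2 × (1/20 + 1/10)) = 0.548 | 1.10 (55 df) | 1.00 |

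The 24:12 column is the 36 per cohort allowed by Clarification Memorandum #2, split 2:1. If the SD lies between 0.5 and 1.5 log10 (an assumption), the concurrent-sham half-width at 20:10 is 1.10 × 0.5 = 0.55 to 1.10 × 1.5 = 1.65 log10.

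**P-values.** Each schedule v pooled sham is also 20 v 20, with half-width 0.63 SD. An effect just above 0.63 SD in one schedule and just below it in the other would fall on opposite sides of 5%, although the two schedules are nearly equal.

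**Weight of Day 8 in TWA.** Protocol 9.3 says that "at Baseline and days 3, 5, and 8, subjects will provide two saliva specimens". SAP 5.5.1 applies the trapezoidal rule, where "t is the actual study day at the specified timepoint, a is the baseline visit at Day 1, and b is the Day 8 visit". An inner visit has weight (next day − previous day) / (2 × total span). An end visit takes half of its single interval over the span.
- Day 1: 1/7 = 14% (change is zero by definition)
- Day 3: 2/7 = 29%
- Day 5: 2.5/7 = 36%
- Day 8: 1.5/7 = 21%

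Within the SAP 5.1 windows (Days 4 to 6 and 7 to 9), the Day 8 weight runs from 1/(2 × 6) = 8% (visits on Days 6 and 7) to 5/(2 × 8) = 31% (Days 4 and 9).

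**What a Day 8 difference becomes in TWA.** Suppose that light per session is equal, so that the schedules are the same through Day 4. A 1.0 log10 schedule difference at Day 8 then gives, at nominal days, 0.357 × f + 0.214, where f is the share already present at Day 5:
- f = 0: 0.21
- f = 1/3: 0.33
- f = 1/2: 0.39
- f = 1: 0.57

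The documents do not say which f applies.

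**The case against.** The strongest reply is that the plan is coherent on its own terms. The study goal in protocol 4.1.1 is reduction in each dose group compared with sham, and the SAP objective names no between-dose comparison. Assessing reduction as a function of dose can be read as giving each dose's effect v sham. The study is hypothesis generating, with a sample of convenience. An interval of about ±1 SD will hardly guide a choice of schedule. All of this stands as a limit on the point's weight. It does not remove the point: what is missing is an estimate with its uncertainty, which needs no power.

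A reader might infer that no 7-day v 4-day estimate will exist at all. The documents do not support that. PDIFF with no control level gives every pairwise difference, with confidence limits through CL. The gap is that this difference is neither specified in the text nor tabulated, and that it ignores the concurrent shams.

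A reader might also infer that TWA dilutes the benefit of the longer schedule three- to five-fold. That needs two facts that are not visible: equal light per session (the figures are redacted) and little or no effect by Day 5. Protocol 4.1.2 speaks of escalating dose cohorts and allows Cohort 2 to run at reduced frequency, in which case the arms could differ from Day 1. The Day 5 window also reaches Day 6. The ratio compares means only: Day 8 change and a time average have different SDs, so no loss of signal relative to noise is shown. TWA is a legitimate choice of estimand, and Day 8 viral load, ≥95% reduction and clearance are already summarised by arm, though without between-arm differences or intervals for them.

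**Conclusion.** The point holds as a gap in estimation and reporting. The protocol raises a dose question. The SAP specifies and tabulates only each schedule v pooled sham, and the one between-schedule figure in its code output is cross-cohort, non-randomised and has no place in the report. The concurrent-sham contrast is better because it rests on the randomisation within each cohort and uses only data already collected. It removes cohort shifts that act equally on active and sham subjects.

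Its precision is limited to about 1.10 SD either side at 20:10 and 1.00 SD at 24:12, assuming a common SD and full follow-up. The weight of Day 8 in TWA (21% at nominal days, 8% to 31% within windows) is a reason for a supportive Day 8 row and not a fault in the primary endpoint. A 1.0 log10 difference at Day 8 would appear in TWA as 0.21 to 0.57 log10 under the assumptions shown, and no single dilution factor should be quoted.

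**What to change.** 1. In SAP 5.5.1, code treatment as four groups: 4-day, Cohort 1 sham, 7-day and Cohort 2 sham, with baseline log10 viral load as covariate.
2. Add to Table 14.2.1.1 the estimate (7-day minus Cohort 2 sham) minus (4-day minus Cohort 1 sham) for TWA, with its 95% CI, and state the expected precision in the SAP.
3. As a supportive row, give the same contrast for baseline-adjusted change at Day 8.
4. Label any direct 7-day v 4-day difference as cross-cohort and non-randomised.
5. State that differing v-sham p-values are not evidence of a dose effect.

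The pooled-sham comparisons can stay as they are. The cost is a small recoding (one more ESTIMATE line in the three-level model is not enough, because that model has no cohort-specific sham), one extra ANCOVA for Day 8 and two table rows. The interim version of Table 14.2.1.1 is already to compare 4-day with Cohort 1 sham. No new data, visits or subjects are needed. The downside is a wide interval, which the report should show plainly.

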7 STUDY POPULATION

The study population is individuals infected with SARS-CoV-2 who have symptoms associated with COVID-19 that is either not under active medical treatment or is being treated as an outpatient. Study subjects must be symptomatic for 3 days or less and have a positive COVID-19 antigen test using an FDA authorized SARS-CoV-2 antigen diagnostic test at or within the past 24 hours of screening. Study subjects will be randomized to treatment arm within dose in a 2:1 ratio according to a fixed schedule using a permuted block design. The targeted number of subjects randomized per dose is 30 (20 volunteers to the RD-X19 arm, 10 subjects to the sham arm). This is a sample size of convenience as this is a hypothesis generating study.

The target population should reflect the subject population with uncomplicated COVID-19 in the community at large.

Subject Inclusion and Exclusion Criteria must be confirmed by a study clinician, licensed to make medical diagnoses.

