9 STUDY ASSESSMENTS AND PROCEDURES

9.1 Screening Assessments

9.1.1 Screening Procedures

At the screening visit, and prior to any other study-related activities, the participating clinical site PI or appropriate sub-investigator will provide the subject with detailed study information and will obtain written informed consent (see section 11.1.1 for more details).

Subject numbers will be assigned with the three-digit numerical site number beginning with numbers greater than one hundred (e.g. 101) followed by an alphanumeric cohort identifier (e.g. C1) and finally a two digit unique numerical identifier assigned with each new subject (e.g. 01).

Example Subject Number: 101-C1-01

COVID-19 Screening

Eligible subjects presenting with uncomplicated COVID-19 must have an oral temperature of at least 100 °F or have at least two moderate or severe symptoms (cough, nasal congestion, or sore throat, headache, chills/sweats, muscle or joint pain, fatigue, or nausea) and consent to be randomized within 3 days of first symptom onset. The subjects will self-assess their COVID-19 symptoms as none (0), mild (1), moderate (2), or severe (3) during screening.

Additionally, subjects who identify with symptomatology associated with COVID-19 will be screened by taking a nasal culture and analyzed for the presence of SARS-CoV-2 by an FDA authorized SARS-CoV-2 antigen test (e.g. BD Veritor™ Plus System, AccessBio Carestart). These systems allow for rapid detection of SARS-CoV-2 via immunoassay for the direct and qualitative detection of SARS-CoV-2 antigens. Subjects presenting at the time of screening that have tested positive via a SARS-CoV-2 rapid antigen test within the past 24 hours and can provide documentation confirming proper identification, the date of the test and testing location, positivity of the result, and name/identity of the assay used to generate the result, are also eligible for enrollment.

There is a small amount of risk to subjects who report mild-to-moderate symptomatology consistent with COVID-19 may have an unknown health problem or co-morbidity at the time of screening that can lead to worsening of condition or hospitalization during study.

General Screening

Some or all of the following assessments are performed during the screening visit to determine eligibility requirements as specified in the inclusion and exclusion criteria:

- Obtain medical history focusing on conditions per protocol exclusion criteria.

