5.5.2 Analysis of Secondary Efficacy Endpoints

The following 6 secondary efficacy endpoints will be summarized using descriptive statistics by visit, as appropriate:

- log10-transformed Viral load as measured in saliva by RT-qPCR at each visit by RT-qPCR
- proportion of subjects with $\geq 95\%$ reduction in SARS-CoV-2 viral load by RT-qPCR at each visit
- time to clearance of viral infection in saliva via RT-qPCR
- proportion of subjects demonstrating clearance of viral infection via RT-qPCR at Day 8/ET visit
- COVID-19 composite severity score at each visit
- time to alleviation of COVID-19 symptoms, defined as the number of hours from the first dose to the first time when all eight symptoms had been assessed by the subject as none (0) or mild (1)
- time to sustained alleviation of COVID-19 symptoms, defined the number of hours from the first dose to the time when all eight symptoms had been assessed by the subject as none (0) or mild (1) and no single symptom reoccurs later at a level above mild (1).

Both time to alleviation of COVID-19 symptoms and time to sustained alleviation of COVID-19 symptoms will be derived from self-assessment by study subjects and recorded on the subjects' diary cards.

For log10-transformed viral load data, geometric means will be computed by exponentiating (base 10) the group means of the log10-transformed viral load. Time-to-event variables will be evaluated using the Kaplan-Meier method and p-values for treatment comparison will be provided via log rank test.

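### The two symptom-alleviation log-rank tests ignore the Day 1 severity score; a score-adjusted Cox model beside them is a cheap improvement, with onset day as a sensitivity analysis only

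*Combined protocol and SAP*

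**What the plan says.** **Symptom endpoints.** For the time-to-event variables SAP 5.5.2 plans Kaplan-Meier summaries, and "p-values for treatment comparison will be provided via log rank test". The shells of Tables 14.2.5.1 and 14.2.5.2 give the number censored, the quartiles, the median with its interval, and a p-value for each active arm against sham. They contain no covariate, stratum or hazard ratio.

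**Baseline severity.** Protocol 9.1.1: "The subjects will self-assess their COVID-19 symptoms as none (0), mild (1), moderate (2), or severe (3) during screening". Protocol 9.3.1: "The COVID-19 Severity Score is defined as the sum of all the individual symptom severity scores", divided by eight. The schedules in Protocol 4.2 and SAP 7.1 place the score on Day 1 and Day 8, and Table 14.2.4 summarises its baseline value by arm.

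**Primary endpoint.** SAP 5.5.1 uses an ANCOVA "with baseline viral load on log10 scale as a covariate and treatment group as an independent variable", coded as "model aval = trt base /ss3". Sham is a single group over both cohorts: "TRT denotes treatment group with values 1 for 4 Days RD-X19, 2 for 7 Days RD-X19, and 3 for Sham".

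**Onset.** Protocol 7: "Study subjects must be symptomatic for 3 days or less". Protocol 9.1.1 asks that subjects "consent to be randomized within 3 days of first symptom onset". Neither Table 14.1.3 nor any listing shell shows an onset date or days since onset.

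**Context.** Randomisation is stratified by site only (SAP 3.1). SAP 5.1 calls the p-values descriptive and says the study is not powered for testing.

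**The concern.** Time until all eight symptoms are none or mild depends on how bad they were at entry. Inclusion criterion 2 admits a subject on a fever of at least 100 °F or on two symptoms graded moderate or severe. One subject may therefore start with eight severe symptoms, while another, admitted on fever with only mild complaints, already satisfies the event definition. The log-rank treats both alike. The SAP sees the parallel problem for viral clearance: Table 14.2.3 leaves out subjects already clear at baseline. The alleviation tables have no such rule and no adjustment.

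At stake are the efficiency of the symptom comparisons and how they read if the arms happen to start at different severity. With 20 subjects per group (10 sham at the Cohort 1 interim) and no stratification on severity, such differences will be common.

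A weaker version of the question applies to the primary ANCOVA. Within the 3-day entry window, the same baseline viral load may be rising in one subject and falling in another, so days since onset might add information.

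**Working it through.** The documents give no power figure, effect size or prognostic strength, so there is nothing to reproduce. Everything below on prognostic strength is an assumption, shown as a range.

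**1. Chance imbalance in one baseline factor, in SD units.** The standard error of the arm difference is √(1/n₁ + 1/n₂).
- 20 v 20 (final, pooled sham): √(0.05 + 0.05) = 0.316. P(|difference| > 0.3 SD) = P(|Z| > 0.949) = 34%.
- 20 v 10 (Cohort 1 interim): √(0.05 + 0.10) = 0.387. P(|Z| > 0.775) = 44%.

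On the log-hazard scale a 0.3 SD imbalance shifts the treatment hazard ratio by a factor of roughly (covariate HR)^0.3: 1.35^0.3 = 1.09, 1.65^0.3 = 1.16, 2.23^0.3 = 1.27.

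**2. Log-rank against Cox adjusted for one covariate.** Assumptions: exponential times, sham median 5 days, censoring at 7 days, true treatment HR 2.5, standardised covariate, two-sided 5%, 3,000 simulated trials per cell. Monte Carlo error is at most √(0.25/3000) = 0.9 points.

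| Covariate HR per SD | 20 v 20: log-rank → Cox | 20 v 10: log-rank → Cox |
|---|---|---|
| 1.00 | 71.6% → 70.0% (−1.6) | 50.2% → 47.3% (−2.9) |
| 1.35 | 65.9% → 69.4% (+3.5) | 47.2% → 47.7% (+0.5) |
| 1.65 | 60.7% → 68.0% (+7.3) | 41.1% → 46.7% (+5.6) |
| 2.23 | 48.7% → 66.0% (+17.3) | 32.1% → 44.6% (+12.5) |

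With no treatment effect, rejection was 4.9% to 5.9% for the log-rank and 5.1% to 6.0% for the Cox model.

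A second set of assumptions (true HR 2, median 84 h, follow-up 168 h) points the same way. With a severity HR of 0.5 per SD (1/0.5 = 2.0 in the table's direction), power rises from 34% to 45% (20 v 20) and from 23% to 31% (20 v 10). At 0.7 per SD (1/0.7 = 1.43) the gain is 2 to 4 points.

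**3. Onset day in the primary ANCOVA.** With N subjects and G groups, adding one covariate to a model that already has one multiplies the variance of the treatment contrast by (1 − R²) × [1 + 2/(N−G−3)] / [1 + 1/(N−G−2)], where R² is the added covariate's partial R².
- Final, N = 60, G = 3: (1 + 2/54)/(1 + 1/55) = 1.0185. Break-even R² = 1 − 1/1.0185 = 1.8%.
- Interim, N = 30, G = 2: (1 + 2/25)/(1 + 1/26) = 1.040. Break-even R² = 3.8%.

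Simulated reduction in residual variance from adding onset day, under assumed rise-and-fall kinetics:
- six scenarios with peak 0 to 2 days after onset: 8% to 28%;
- peak 1 to 2 days after onset: 15% to 38% with day-0 entrants, 1% to 15% without;
- peak around onset (SD 1 day), no day-0 entrants: 0.3% to 1.7%;
- peak at onset or about a day before: 0.2% to 1.4%.

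The range falls on both sides of break-even.

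If onset day is uniform on 0–3 or 1–3 days, the chance difference in its mean has SD 0.26 to 0.35 day (20 v 20) or 0.32 to 0.43 day (20 v 10).

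**The case against.** The strongest reply is that the study is hypothesis-generating with descriptive p-values, that the log-rank is valid under randomisation, and that further covariates are a matter of judgement. Much of this stands. Intervals from a randomised comparison already allow for chance imbalance, and the simulated type I error is intact. The gain exists only if severity is prognostic, which the documents do not quantify; at the interim a covariate HR of 1.35 per SD yields almost nothing. The adjusted hazard ratio is also conditional on the score, so it need not match an unadjusted one even with balanced arms.

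The reply does not remove the point for the symptom endpoints. The score is built from the same eight items that define the event, it is already scheduled on Day 1, and the cost of a wrong guess is small.

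A reader might go further and infer that the primary ANCOVA also loses precision by omitting onset day and leaves disease stage uncorrected. The documents do not support that:
- Baseline viral load is already in the model and onset is capped at 3 days, so part of any stage difference is removed.
- The final comparison uses pooled sham, planned 20 v 20; 10 sham subjects applies only to the Cohort 1 interim.
- Onset timing is checked for eligibility, but no listing shows it held as an analysis variable.
- Under some plausible kinetics the gain is below break-even, and the interval would widen slightly.

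Nor do baseline viral load and severity score need adding to Table 14.1.3. Tables 14.2.2.1 and 14.2.4 already give them by arm.

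**Conclusion.** The point holds for the two alleviation endpoints, as a cheap improvement and not a flaw that invalidates the plan. The planned log-rank tests ignore a baseline measure that is tied to the event by construction. If that measure is prognostic (HR 1.35 to 2.23 per SD), the loss at 20 v 20 is about 3 to 17 points of power under the stated assumptions, and chance imbalance in starting severity stays in the comparison. If it is not prognostic, adjusting costs about 2 points. It is not a source of inflated false positives.

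For the primary ANCOVA only a modest statement is supported: days since onset may or may not help, depending on kinetics the documents do not give. It needs more than about 2% partial R² to break even at the final analysis and about 4% at the interim. That justifies a sensitivity analysis, not a change to the primary model.

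**What to change.** **Main change, SAP 5.5.2.** For both alleviation endpoints, prespecify a Cox model with treatment group and the Day 1 severity score (last value before first treatment) as covariates. Report the adjusted hazard ratio of each active arm against sham, with its 95% interval, beside the planned log-rank in Tables 14.2.5.1 and 14.2.5.2. State in the SAP how subjects who already meet the event before treatment are counted, and use the same rule in both analyses. The cost is SAP wording, a few table rows and one model degree of freedom. Because both endpoints are in the Cohort 1 interim, the text should be settled before that unblinding; if that has passed, date the addition and label it as such.

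**Secondary step.** Where onset date can be obtained from source, add days from symptom onset to first treatment to Table 14.1.3, and prespecify `model aval = trt base onsetday` as a sensitivity analysis of the primary ANCOVA, not a replacement. This costs one further model term and, if the eCRF has no field for onset date, retrieval and entry of that date.
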